## **Study Entry and Recruitment**

Subjects with stress incontinence or stress-predominant mixed urinary incontinence who are scheduled to undergo a retropubic midurethral sling with or without concomitant anterior repair at West Penn Hospital, Bethel Park Health and Wellness Pavilion, Wexford Health and Wellness Pavilion, and Jefferson Hospital of the Allegheny Health Network, will be offered participation in the study. Study subjects may also be recruited via the MyChart app. The MyChart app is a secure app accessible only by the patient. Only the patient can access their medical information through this app by setting up a secure account using their social security number, birthday, username, and password. The patient can log in securely by providing their username and password, or via biometrics (i.e., face recognition). If the research staff reaches out to the subject via telephone and the subject does not answer, a follow-up message will be sent to the subject via the MyChart app, with the statement that initial contact attempt was made by phone. The message will include the following:

A recent review of your records indicated that you may be eligible to participate in an ongoing research study. The Retropubic Lidocaine study is looking to determine if the numbing medicine we standardly use during surgery impacts your ability to empty your bladder postoperatively. If you are interested in participating, you would be randomly selected to get our standard numbering medicine (lidocaine and epinephrine) or placebo (saline and epinephrine) at the two sling exit sites in your pubic area while in the operating room. This study does not require any additional in-person visits. There will be a few questionnaires we would ask you to complete during your recovery. If you are interested in learning more about our study, please call [contact], or email [contact]. If you respond to this message indicating your interest, you are giving your permission for the study staff to receive your phone number and/or email address indicated in your medical records and reach out to you directly.

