Inclusion criteria includes the following: age 18 years or older, English speaking, and competent to give consent. Exclusion criteria includes a known intolerance or allergic reaction to local anesthetics, planned spinal anesthesia for the procedure, planned concomitant prolapse repair other than anterior repair, or preoperative voiding dysfunction as evidenced by a post-void residual (PVR) of 150 mL or greater. On average, our institution treats 60-80 patients per year with midurethral slings.

Informed consent will be obtained at the preoperative appointment. Demographic information including age, weight, height, body mass index (BMI), allergies, obstetrical, gynecological, medical, and surgical history will be collected from those subjects who agree to participate. Preoperative bladder testing obtained as part of routine clinical care will also be recorded,

Patients will be randomized in the preoperative area on the day of surgery to prevent randomization of patients who may go on to cancel or postpone surgery. Randomization will be created using a random numbers table with blocking into groups of 4. On the day of surgery, the operating room pharmacist will prepare 20 cc of either study drug, 0.5% lidocaine with epinephrine 1:200,000, or normal saline with epinephrine 1:200,000 in identical appearing 20cc syringes to be injected retropubically. Our group's routine clinical practice will inject the randomly assigned 20cc syringe retropubically along the path of the midurethral sling trocars. Suburethral injection of local anesthetic will be performed at surgeon discretion. Surgical teams, anesthesia teams and patients will be blinded to allocation assignment. The investigational drug pharmacist will maintain the randomization sequence.

Standard postoperative care will then be followed. Before discharge, as part of routine clinical care, all subjects will undergo a postoperative voiding trial as outlined below. A routine postoperative evaluation will be performed by the primary surgeon at a 6-week interval following surgery.

Table 1. Timeline of data collection

	Time of Data Collection/Eval						itions	
Data	Baseline	Intervention	Surgery	Pos	stoperative as			
				2 h	6 h	24h	Week 1	Week 6
				(+-30	(+- 30			
				mins)	mins)			
Retrograde Voiding Trial				Х				
VAS pain score	Х			Х	Х			
Narcotic requirements	Х		Х	Х	Х	Х	х	
Pain Diary						Х	х	
Demographic factors	Х							
Intraoperative factors			Х					
Side effects (APS-POQ-R)						Х		

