# **Sample Size Calculation**

The rate of postoperative urinary retention following midurethral sling at our institution is 35% (data unpublished). To detect a clinically significant reduction of postoperative urinary retention of 20%, 72 subjects per group would be needed to provide 80% power with a two-sided alpha of 0.05. After adjusting for a 5% loss to follow-up rate, 75 subjects per arm would be required.

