## **Data and Statistical Methods**

**Aim 1**: to compare the incidence of urinary retention following retropubic midurethral sling placement in those women receiving normal saline vs lidocaine for retropubic hydrodissection. Rates of postoperative urinary retention will be compared between groups using chi squared testing. Duration of urinary retention measured in days will be compared using t-tests or nonparametric testing as appropriate. To adjust for other factors that may impact voiding trial results, logistic regression analysis will be performed and will include variables identified as significant (p>0.01) on univariable analysis as well as intraoperative narcotic use, age, and estimated blood loss. All analyses will be performed using intention to treat. Data analyses will be done using SPSS and Matlab.

**Aim 2**: to assess postoperative pain in women receiving retropubic normal saline vs lidocaine during midurethral sling placement. VAS scores will be measured on a scale of 0-100mm with higher scores indicating worse pain. Change from baseline in VAS pain scores will be compared at each time point with t-tests. Narcotic requirements measured in morphine equivalent grams will be compared by t-tests (and

Wilcoxon rank-sum tests if non-parametric). Both VAS pain scores and narcotic requirements will be compared in an intention to treat analysis. Multivariable logistic regression analyses will be used to identify independent risk factors that predict pain at 2, 6 and 24 hours postoperatively. We plan to adjust for operating time, estimated blood loss, urinary retention, and concomitant procedures, as all of these may predict worse postoperative pain. Anything found to be different at baseline will also be included as covariates.

**Aim 3**: to assess patient satisfaction in women receiving retropubic normal saline vs lidocaine during midurethral sling placement. Patient satisfaction Likert scale questionnaires will be compared using t-tests with lower scores indicating worse satisfaction. T-tests (and Wilcoxon rank-sum tests if non-parametric) will be used to analyze results of individual APS-POQ-R questions.

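### Naming site in the randomization and in the primary test would be a cheap improvement: four sites, no stratification stated, and a chi-squared test that ignores site

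*Combined protocol and SAP*

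**What the plan says.** Study Entry and Recruitment lists the places of surgery: "West Penn Hospital, Bethel Park Health and Wellness Pavilion, Wexford Health and Wellness Pavilion, and Jefferson Hospital". The same section gives the allocation method: "Randomization will be created using a random numbers table with blocking into groups of 4". No stratification factor is named. On custody it adds: "The investigational drug pharmacist will maintain the randomization sequence". The noun is singular, but the text does not say whether there is one central list or one per site.

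Data and Statistical Methods, Aim 1, sets the primary comparison: "Rates of postoperative urinary retention will be compared between groups using chi squared testing". The supporting logistic regression always includes intraoperative narcotic use, age and estimated blood loss. Site is not among these and could enter only through the univariable screen.

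Sample Size Calculation makes no allowance for site.

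**The concern.** Site is known for every woman before she is randomized, and practice may cluster by site. The protocol leaves suburethral anesthetic to the surgeon and allows anterior repair as an option, and either could follow the surgeon or the building. If one list serves all four sites, consecutive places in a block can go to different sites. The blocks then balance the total but not the arms within a site.

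Three things follow if retention differs between sites. Between-site variation goes into the error of the primary comparison, chance imbalance within sites moves the estimate, and a test that uses site would be somewhat more powerful.

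There is little slack in the plan. The sample size only just reaches its power target. Recruitment is also tight: 60-80 sling patients a year over two years is 120-160 women before exclusions and refusals, against the 150 needed. Power that costs no patients is worth having.

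**Working it through.** **1. The plan's own sample size.** Inputs from Sample Size Calculation: an institutional retention rate of 35%, a two-sided 5% level, a power target of 80%, and this effect and size: "To detect a clinically significant reduction of postoperative urinary retention of 20%, 72 subjects per group would be needed". Reading 20% as an absolute reduction (35% v 15%, mean 25%), with pooled variance and no continuity correction:

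n = [1.96·√(2·0.25·0.75) + 0.842·√(0.35·0.65 + 0.15·0.85)]² / 0.20² = (1.200 + 0.501)² / 0.04 ≈ 72.4

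This rounds up to 73, against 72 stated, so the figure reproduces. Power at 72 per group is 79.8%. At 75 per arm it is 81.4%. After 5% loss, 75 × 0.95 = 71.25, and 71 per arm gives 79.2%.

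**2. Imbalance within sites if there is one list.** Take 144 women (72 per group) and a site with share w. Each woman adds ±1 to the arm difference in her site, and two women in the same block of 4 have correlation -1/3. The variance of the difference is then 36 × [4w - 12w²/3] = 144·w(1-w), and the mean absolute difference is about 0.80 × SD. The shares are assumed.

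| Site share | SD of difference | Mean absolute difference | 95th percentile (simulated) |
|---|---|---|---|
| 50% | 6.0 | 4.8 | 12 |
| 25% | 5.2 | 4.1 | 10 |
| 20% | 4.8 | 3.8 | 9 |
| 10% | 3.6 | 2.9 | 7 |

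The simulated chance that at least one site differs by 8 or more women is about 42% with equal sites and about 36% with 50/20/20/10 shares. With one block-of-4 list per site, the mean is 0.7 and the difference cannot exceed 2.

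**3. What that does to the estimate.** With N = 150 and site rates of standard deviation σ, imbalance shifts the estimated difference with SD of about 2σ/√150. The standard error of the difference at 75 per arm is √(0.355/75) = 6.9 points. Assumed site rates, each set averaging 35%:

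- 25, 30, 40, 45%: σ = 7.9, shift SD 1.3 points
- 20, 30, 40, 50%: σ = 11.2, shift SD 1.8 points
- 10, 30, 50, 50%: σ = 16.6, shift SD 2.7 points

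**4. Power.** Simulation with N = 150, four equal sites, a constant odds ratio, 35% v 15% overall and 12,000 trials per row:

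| Assumed site rates | One list, chi-squared | Per-site lists, CMH | Change |
|---|---|---|---|
| No difference | 82.7% | 81.7% | -1.0 |
| 25-45% | 81.8% | 82.7% | +0.9 |
| 20-50% | 81.9% | 83.6% | +1.7 |
| 10-50% | 82.5% | 85.3% | +2.8 |

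Simulation error on each power is √(0.82·0.18/12000) = 0.35 points, so about 0.5 on a difference. The first two rows are therefore close to noise. Other runs with different site patterns gave ranges of about 1-3 points at 20-50% and 3-4.5 points at 10-50%. A gain near 6 points appeared only with lidocaine-arm rates of about 21% v 67% and unequal site sizes.

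Most of the gain comes from the analysis. In the 10-50% case, keeping one list and using CMH gives 85.1%.

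**5. Type I error.** With one list and the planned chi-squared test, null rejection was 4.6-5.1% in every scenario at N = 144. With per-site lists and the chi-squared test left unchanged, it fell to about 3.2% under strong site differences (14% v 56%, or 21% v 67%) and 4.1% with site rates of 10-50%. CMH after per-site lists stayed near 5%.

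**The case against.** The strongest reply is that blocked, unstratified randomization followed by a chi-squared test is a valid and common design. That stands. Under one list, chance imbalance by site is already part of the sampling error the test allows for, so it is not a second threat on top of the standard error.

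It is also fair to say that nothing in the documents shows that sites differ. The voiding trial has a fixed fill, time limit and pass threshold. Spinal anesthesia and other prolapse repairs are excluded. The only rate given is one institutional 35%. The 10-50% in the Background is a general range for women having slings, not a range across these sites. It serves here only as a wide assumption.

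The logistic regression might admit site through its screen. But that is a supporting analysis and depends on the data, so it does not answer the point for the primary test.

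A reader might infer more than the text supports:

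- **That the four sites share one list.** The singular wording suggests it, but the protocol does not say so.
- **That power is certainly being lost.** That depends on site differences the documents do not report. With none, the fix gains nothing and may cost about 1 point.
- **That the planned test is biased or invalid.** It is not; its error rate holds under one list.

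What survives is that the plan needs attention under either reading. With one list, precision may be lost. With per-site lists, the chi-squared test is conservative when sites differ.

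**Conclusion.** A cheap improvement, not an error. The documents establish four sites, no stated stratification and a primary test that ignores site. They do not establish that retention varies by site.

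The gain in power from the fix is about 0-1 point if site rates span 20 points or less, about 1-3 points for 20-50%, and about 3-4.5 points for 10-50%. These figures assume 144-150 women, a constant odds ratio and 35% v 15% overall, with site rates and shares that are assumed.

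For scale, by the formula in step 1 power rises from 81.4% at 75 per arm to 83.8% at 80 and 84.7% at 82. A 3-point gain is therefore worth roughly six women per arm.

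**What to change.** - **Study Entry and Recruitment:** state that the investigational drug pharmacist holds one block-of-4 list for each of the four sites.
- **Data and Statistical Methods, Aim 1:** make the primary test a CMH test stratified by site, and include site in the logistic model whatever the univariable screen shows.

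Make the two changes together, because per-site lists with an unstratified chi-squared test would be conservative. If enrolment has started, leave the randomization alone, state which kind of list was used, and make the analysis change before unblinding. The Data and Safety Monitoring Plan describes an early look at failed voiding trials by arm, so the change is best dated before that look.

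The cost is four short lists instead of one and a few sentences of text, with no extra women, visits or data. The downsides are an imbalance of at most 2 women per site from incomplete blocks, and up to about 1 point of power if sites do not differ.

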#### Variables and measures

## Postoperative Urinary Retention

The primary outcome is postoperative voiding trial failure, defined as being discharged from the hospital with an indwelling catheter or instructions for clean intermittent self-catheterization (CISC). Duration of catheterization will also be measured and recorded on the postoperative diary. As part of routine clinical care, a retrograde voiding trial will be completed 1-2 hours postoperatively using the following protocol and parameters:

# Retrograde Voiding Trial:

- Confirm that all urine is drained from the bladder with the indwelling catheter in place
- Backfill 300 mL of sterile saline into the bladder through the indwelling catheter
- Clamp catheter, deflate the balloon, and remove the catheter
- The patient should be asked to void within 1 hour into a urine collection container in the toilet
- Record voided volume

Passed void trial: patient voids at least 200 mL Failed void trial: patient voids <200 mL or cannot void at all within 1 hour of test

In the event that all 300 mL of sterile saline are unable to be instilled into the bladder due to patient discomfort or bladder spasms, the test is still considered passed if >2/3 of instilled bladder volume is voided.

All patients who meet criteria for failure as described above are discharged from the hospital with either an indwelling catheter or CISC.

#### Postoperative pain

Visual Analog Scale (VAS) pain: Pain will be measured 2 hours (+/- 30 Minutes) and 6 hours (+/- 30 minutes) following surgery by VAS pain scales. VAS pain scales are unidimensional measures of pain intensity that are easily completed and scored. Subjects place an "X" on a 10-centimeter (cm) VAS line at the point that represents their pain intensity. The score is calculated by measuring the distance in millimeters (mm) along the 10 cm line where 0 represents "no pain" and 10 represents "worst pain." Scores range from 0-100mm. They have been widely used in diverse populations to assess pain. VAS pain scores will be used as the outcome measure in this study because they are easy to complete and because they are easily compared to prior studies. The 2-hour VAS score will be completed prior to discharge. The 6-hour VAS score will be returned via mail since patients are routine discharged a few hours after sling surgery.

Pain diary: Pain diaries will also be used in order to assess postoperative pain in the home setting. Pain diaries will be provided to all participants at time of discharge to be completed from POD #0 until postoperative day #7. Patients will be asked to register their pain intensity at home on a VAS scale once every morning and every evening. These will be returned by the patient via mail in self-addressed stamped envelopes.

#### Narcotic requirements

Morphine equivalents: Doses of narcotic pain medications administered to subjects during the intra- and postoperative period will be abstracted from the EMR. Narcotics will be converted to morphine equivalents, in grams, using an equianalgesic dosage table. Narcotic use following hospital discharge will be measured by a 7-day diary, which will also be converted to morphine equivalents. Morphine equivalents have been widely used in the study of postoperative pain.

#### Patient satisfaction and mood

APS-POQ-R: The APS-POQ-R is a validated questionnaire used to assess QOL and satisfaction with pain control over the 24 hours following an operation. It is preferred over more global measures of QOL since it is validated for acute pain in the setting of recent surgery. This questionnaire was designed to assess satisfaction with pain control and impact of pain on mood and emotional well-being. It contains twelve items across six subscales: pain severity and relief, impact of pain on mood/emotions, adverse effects, satisfaction, participation in decision making, and non-pharmacological methods of pain management. We are specifically interested in the impact of pain on satisfaction (item 9), mood/emotions (item 5 a-d) and adverse effects (item 6 a-d, see below). These subscales use a 0-10 rating scale. This measure has good internal consistency (alpha=0.85) and validity.

#### Patient satisfaction

Likert Scale: The Likert Scale is the most widely used approach to scaling responses in survey research and contains five tiered responses which users quantify on a visual analogue scale. The administration of such is easily comprehended, provides an effective and clinically relevant means of assessing patient satisfaction, and can readily be used in clinical practice. To determine satisfaction, patients will be asked to rate their satisfaction with surgery on a Likert scale (with 1 being the least satisfied and 5 being the most) at their 6-week postoperative follow up visit.

# **Sample Size Calculation**

The rate of postoperative urinary retention following midurethral sling at our institution is 35% (data unpublished). To detect a clinically significant reduction of postoperative urinary retention of 20%, 72 subjects per group would be needed to provide 80% power with a two-sided alpha of 0.05. After adjusting for a 5% loss to follow-up rate, 75 subjects per arm would be required.

## **Data Collection & Storage**

The patient's electronic medical record will be reviewed for demographic and surgical information. Data entry will be completed and stored on a password protected network drive within the health system firewalls. Each patient will be assigned an alphanumeric code for data collection. The key linking patients with their respective codes will be recorded in an encrypted file on password-protected computer in the research coordinator's locked office. The de-identified parameters will be tabulated in Excel spreadsheets. Security will be maintained by limiting login access to members of the study team. Data security will be monitored at monthly research meetings.

## Potential Risks, Issues, and Solutions

General risks associated with the study include the possible loss of confidentiality and increased pain secondary to lack of lidocaine in the placebo arm. Since clinical practice regarding retropubic lidocaine varies widely and many surgeons do not use lidocaine or do not use any form of hydrodissection retropubically, we do not think that a placebo of normal saline is unreasonable or places the patient at undo risk. Because both placebo and study drug will contain epinephrine, bleeding risk should not differ between the groups.

Patients that do not undergo surgery after enrollment: To prevent non-adherence to the study intervention, we will not randomize subjects until the day of surgery in the preoperative area. Once randomized, all participants will be followed and analyzed in an intention to treat analysis. Subjects who are lost prior to randomization, for example those that cancel surgery or are not medically cleared will be excluded from analysis.

Competing events: We plan to exclude those women with severe dementia that will be unable to accurately complete study questionnaires/VAS pain scores. Because patients with terminal diseases or those expected to have poor follow-up do not usually receive elective sling surgery, these events should not occur in a high percentage of subjects, if at all.

Missing data: Subjects with missing void trial results or those that do not complete/return questionnaires and diaries will still be included in the final analysis. To reduce the chance of missing data, members of the study team will call subjects or personally visit them in their hospital room to provide reminders for completion of VAS pain scales and APS-POQ-R questionnaires. Study nurses will call the patient at 1 week to remind them to complete and return their pain diary. We will also emphasize the importance of the data and need for completeness with subjects at the time of enrollment. By keeping data collection short (limited short forms with study participation ending on POD#7), we will not overburden the subjects.

# **Study Duration**

This study will include patients who undergo midurethral sling placement. Enrollment for this study is expected to last for two years in order to achieve adequate sample size. Once enrolled, patients will be followed from date of surgery until six week postoperatively.

Tab	le 2.	. Time	line
-----	-------	--------	------

	Year 1			Year 2			Year 3					
	Q 1	Q2	Q3	Q4	Q1	Q2	Q3	Q4	Q1	Q2	Q3	Q4
Train research staff												
Baseline data collection												
Follow-up data collection												
Analysis												
Write manuscript												
Disseminate findings												

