Our current practice of midurethral sling placement involves injection of lidocaine with epinephrine into the retropubic and suburethral space with the threefold purpose of hydrodissection, hemostasis, and pain reduction. Interestingly, several studies report varying rates of postoperative urinary retention and postoperative pain depending on the type of local anesthetic used (if any) for hydrodissection: however. the data is sparse and invites a more thorough investigation. For example, one study investigated the use of bupivacaine versus normal saline injected suburethrally on postoperative voiding function and pain in patients undergoing retropubic midurethral sling. These authors found no difference in voiding dysfunction between the study and placebo groups; however, the use of bupivacaine did lower pain scores at 6 hours postoperatively. A similar study compared urinary retention and pain control when bupivacaine versus saline for hydrodissection is used while placing tension-free vaginal tape midurethral slings. Hydrodissection fluid was placed subcutaneously, into the space of Retzius bilaterally, suburethrally, and periurethrally. These authors concluded that bupivacaine did not increase the risk of failing a postoperative voiding trial; however, there was a trend toward a difference with a 19% reduction in voiding trial success (47% pass rate in the bupivacaine group vs 66% in the saline only cohort, p = 0.14) and a statistically significant elevated PVR in the bupivacaine group compared with the control group. In addition, bupivacaine was not seen to improve immediate postoperative pain after placement of a tension-free vaginal tape. A third study reported that while bupivacaine did decrease postoperative pain scores following retropubic midurethral sling placement, reported pain was in fact low in both the intervention and placebo groups. Of note, there was also a trend toward increased voiding trial failure in the bupivacaine group (33% vs 18% in the controls (p = 0.082)). In this study, injections were performed into each of the two trocar paths "deep behind the pubic bone" and into the vaginal incision.

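### Can 150 patients be enrolled in two years when the plan reports 60-80 sling patients a year?

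*Combined protocol and SAP*

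**What the plan says.** Three statements bear on this, all in the combined protocol and SAP.

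- Sample Size Calculation: "After adjusting for a 5% loss to follow-up rate, 75 subjects per arm would be required". Two arms make 150.
- Study Entry and Recruitment: "On average, our institution treats 60-80 patients per year with midurethral slings". The same section recruits at "West Penn Hospital, Bethel Park Health and Wellness Pavilion, Wexford Health and Wellness Pavilion, and Jefferson Hospital of the Allegheny Health Network", four sites of one network. It does not say whether the annual figure covers one of them, some or all.
- Study Duration: "Enrollment for this study is expected to last for two years in order to achieve adequate sample size".

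The plan gives no eligibility fraction, consent rate or month-by-month accrual projection. Table 2 sets out a three-year timeline, but its cells cannot be read in the text available, so it settles nothing either way.

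**The concern.** Put side by side, the volume and the duration seem not to fit. At the midpoint of the stated range, two years bring in fewer sling patients than the trial has to randomise, even if every one of them joins. Not every one can. Study Entry and Recruitment excludes, among others, women with "planned concomitant prolapse repair other than anterior repair", a high post-void residual or planned spinal anesthesia, and it requires English and consent.

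If the trial stopped at two years without reaching its target, it would have less power than the 80% claimed for a fall in retention from 35% to 15%. Background/Hypothesis criticises earlier studies as small, so a shortfall here would matter.

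**Working it through.** **Inputs.** Annual volume 60-80 (70 is the midpoint), from Study Entry and Recruitment. Enrolment period two years, from Study Duration. Target 2 × 75 = 150, 35% baseline retention, 20-point reduction, 80% power and two-sided alpha 0.05, from Sample Size Calculation.

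**Step 1: the plan's own figure.** Two-proportion normal formula with pooled variance under the null, 35% against 15%, mean 25%:

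n = [1.96 × √(2 × 0.25 × 0.75) + 0.8416 × √(0.35 × 0.65 + 0.15 × 0.85)]² / 0.20² = (1.2002 + 0.5014)² / 0.04 = 72.4 per arm.

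The plan states 72. The loss allowance gives 72 / 0.95 = 75.8 against the stated 75. Both agree to within one patient per arm, so 150 is a fair target to test.

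**Step 2: supply if 60-80 covers all four sites (assumption).** Share needed = 150 / (2 × annual volume). Time at full capture = 150 / annual volume.

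| Volume per year | Two-year supply | Balance against 150 | Share needed | Years at full capture |
|---|---|---|---|---|
| 60 | 120 | −30 | 125% | 2.50 |
| 70 | 140 | −10 | 107% | 2.14 |
| 80 | 160 | +10 | 94% | 1.88 |

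Break-even at full capture is 150 / 2 = 75 a year. Without the loss allowance (144 patients) the shares are 120%, 103% and 90%, so the loss allowance does not create the gap.

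**Step 3: incomplete capture, same reading.** The plan gives no fraction, so these are illustrations. At 90% capture, 150 / (0.9 × volume) = 2.78, 2.38 and 2.08 years. At 70%, 3.57, 3.06 and 2.68 years.

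**Step 4: the other end of the site question.** If 60-80 were the volume of each site (assumption), two years supply 4 × 60 × 2 = 480 to 4 × 80 × 2 = 640. Then 150 / 480 = 31% and 150 / 640 = 23%, and two years is comfortable. Between these ends, the network volume needed is 75 / capture a year: 75 / 0.7 = 107 at 70% capture, or 75 / 0.5 = 150 at 50%. Moderate extra volume from other sites could therefore remove the gap.

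**Step 5: what depends on the calendar.** Study Duration gives the two years as an expectation, with adequate sample size as the purpose, so time serves the target. The primary outcome is fixed at hospital discharge, and the later measures are timed from each patient's own surgery, up to six weeks. Slower accrual alters none of these. Allocation in blocks of four keeps the arms close in number throughout, so a longer period does not confound treatment with calendar time. At 75 per arm the Step 1 formula gives 81.4% power, or 79.4% with 5% lost (71.25 per arm), however long enrolment takes.

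**The case for a change.** The strongest case for a change is that the plan gives one volume, leaves its scope undefined, and never says outright what ends enrolment. Sample Size Calculation also attributes the 35% retention rate that sizes the whole trial to the institution, which fits the all-sites reading. On that reading even 80 a year leaves room to lose only 10 patients in 160. If enrolment did close at two years, power at full capture would be 72% at 60 a year (60 per arm) and 79% at 70 a year (70 per arm). At 80 a year the target of 150 would be reached first.

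Part of this stands. The scope of the 60-80 is not defined, and on the all-sites reading two years is optimistic. The rest does not carry. An unpublished rate may come from one hospital as easily as from four, so the shared wording does not settle the scope. The power losses belong to a closure at two years that no readable part of the plan sets.

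Nor can the comparison be sharpened by supposing that the 60-80 includes slings other than retropubic ones. The plan uses the unqualified term for the trial procedure itself, as in "Our current practice of midurethral sling placement involves injection of lidocaine with epinephrine into the retropubic and suburethral space" and "This study will include patients who undergo midurethral sling placement".

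**Conclusion.** The multiplication is right, but the conflict is conditional. It appears only if the 60-80 covers most or all of the four sites, which the documents neither state nor rule out. On the all-sites reading the two-year forecast needs 94% to 125% of all sling patients, and 150 takes at least 1.9 to 2.5 years. On the per-site reading the share is 23% to 31%.

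On either reading a wrong forecast costs calendar time and nothing else, because the plan ties enrolment to the sample size and not to a date. The target of 150, the planned power and the analyses are unaffected. Defining the volume would help a reader judge feasibility, but it would alter no result, and a trial team would ordinarily continue to the target. The conclusion assumes that enrolment runs to 150 and that the unreadable Table 2 sets no fixed closing date.
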